Data for our primary outcome of interest, any antipsychotic use, will be collected from electronic health records on provider orders. Electronic health record data on prescription fills will be used to assess the secondary outcome (antipsychotic medication fills). This means that traditional study drop-out due to premature participant withdrawal from the study will not lead to missing data in primary analyses. However, there will be the potential for differential follow-up rates among individuals due to youth disenrolling from their or their parent/guardian's health plan. Death is also a possibility, but unlikely. We will compare those youth for whom we are only able to collect outcome information for a portion of the 6 month follow-up period to those participants for whom we have complete 6 month follow-up information on their demographics, treatment group, and other salient baseline variables. We will account for differential follow-up times due to disenrollment in the Poisson regression model using an offset(46). Because our power calculations are based on excluding all individuals lost-to-follow-up due to disenrollment, these estimates are conservative.

The secondary outcome of emergency department visits will be estimated by Poisson regression in each of the arms, again using generalized estimating equations for the reasons listed above for the primary outcome. The intervention will be compared for non-inferiority to control using a margin of $M=1.5$. This margin of 1.5 for the rate ratio represents a threshold for the relative increase of 50%, beyond which we would consider unacceptable. Sikirica (2014) observed an annual rate of 0.39 per year among adolescents with attention deficit/hyperactivity disorder who were taking antipsychotics(47). Using an estimated rate of emergency department visits of 0.0325 per month on control(47), the non-inferiority margin of 1.5 for the incidence rate ratio would represent a corresponding maximum acceptable rate of 0.0488 per month in the intervention arm. If the rate of emergency department use is greater than expected, say 0.05, then the non-inferiority margin of 1.5 would correspond to a maximum rate of 0.075 in the intervention arm. The estimated treatment effect (emergency department rate on algorithm

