divided by the rate on control, estimated by Poisson regression) and 95% two-sided confidence interval (CI) will be compared to the non-inferiority margin (overall: $M = 1.5$) and non-inferiority of the algorithm approach will be declared if the entire coverage of the 95% CI is less than 1.5.

In safety review reports, the ratio between arms of emergency department visit rates will be accompanied by a confidence interval and by the non-inferiority margin, 1.5, for reference. Confidence intervals will be defined by estimating the rate ratio in 5,000 bootstrap samples. Resampling will be done on the cluster (provider) level and stratified by the presence of any event within each cluster. Quantile-based confidence intervals will be identified using the appropriate percentile corresponding to the Pocock alpha-spending function for interim analyses. Excess harm is observed if the entire coverage of the confidence interval for the rate ratio comparing the greater to the lesser rate of emergency department and urgent care visits is greater than 1.5. (While the final non-inferiority analysis for this safety outcome will use the robust sandwich estimator to ensure correct standard errors, the properties of this estimator are based on asymptotic behavior and small sample size performance may be poor.)

We anticipate initial follow-up of 800 patients, randomized to the two arms, with 720 patients remaining enrolled in the study at 6 months of follow-up (i.e., 10% lost to follow-up). Assuming a $P < 0.05$ alpha level, and based on an anticipated 95% of patients in the control arm using antipsychotics at 6 months, this sample will ensure over 95% power to detect a 6% reduction in the percent of participants with any order for antipsychotic medications at 6 months. Furthermore, we expect to have 80% power to detect a 13% reduction in subgroups with exposures occurring with 25% prevalence, and 80% power to detect a 17% reduction in subgroups with exposures occurring with 18% prevalence (e.g., racial/ethnic minorities). A minimal clinically important difference of 10% was pre-specified to allow for evaluation of clinical significance as well as statistical significance. We have over 90% power to detect a 10% reduction in antipsychotic use at 6 months for patients in the intervention arm given a rate of 85%, 90%, or 95% use in the control arm.

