As these power calculations are based on the assumed percent of participants on any antipsychotic in the control arm and assumed pattern of intervention effects, we provide examples of detectable intervention effects corresponding to alternative scenarios in the table that follows, including varying rates of subgroup prevalence to evaluate power regarding intervention effectiveness in less prevalent minority groups. In summary, at a range of percentages of participants with any antipsychotic use in the control arm, we will have excellent power to detect a variety of clinically meaningful intervention effects within the expected range.

Using an estimated rate of emergency department visits of 0.0325 per month on control(47) and with a one-sided 0.025 alpha level with equal allocation between groups, we estimate 71% power(48) with 400 patients per arm and 67% power with 360 patients per arm (allowing for loss to follow-up) respectively, to detect equality of emergency department visit rates (i.e., a true rate ratio of 1) in a non-inferiority evaluation with a margin of 1.5. With a greater monthly emergency department rate of 0.05, we would have 88% and 84% power with 400 and 360 patients per arm respectively under otherwise equivalent conditions.

Power under varying percentages of participants in each arm taking antipsychotic medication at 6 months (based on medication orders) and under various subgroup prevalence assumptions.

Subgroup prevalence	n per arm*	Intervention	Control	Power
100%	360	89%	95%	80%
100%	360	85%	95%	>99%
100%	360	80%	90%	97%
100%	360	75%	85%	92%
25%	90	82%	95%	80%
18%	65	78%	95%	80%
10%	36	75%	95%	67%
5%	18	65%	95%	62%

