10 ASSESSMENT OF SAFETY

10.1 Specification of Safety Parameters

It is not feasible to report incidental adverse events (AEs) for this pragmatic trial. Study staff do not have contact with control arm patients. Only intervention arm patients have contact with study staff, resulting in an inability to compare rates of incidental AEs between arms.

We will compare the number and rate of emergency room and urgent care visits, inpatient hospitalizations (psychiatric and non-psychiatric), suicide attempt (fatal and non-fatal), and deaths from all causes to monitor for potential harm to subjects. Comparisons of safety signals between arms will be made and reported to the DSMB 3 times per year. The PI and site investigators will be blinded to the results of these assessments.

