10.2 Halting Rules

Study halting may occur as required by the IRB, NIMH, or the NIMH DSMB. The PI may temporarily suspend enrollment pending review by these authorities if warranted based on significantly more safety events occurring in the intervention arm per safety monitoring results.

The study would not be halted early if the intervention was found to be protective (i.e., significantly lower rates of safety events in the intervention arm).

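### The interim harm label ignores direction, is insensitive to ratios moderately above 1.5, and is not reconciled with the halting text or the PI's blinding

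*Protocol*

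**What the plan says.** Protocol 8.2.1 sets a non-inferiority margin of 1.5 for the ED visit rate ratio: "This margin of 1.5 for the rate ratio represents a threshold for the relative increase of 50%, beyond which we would consider unacceptable". The final analysis divides the intervention rate by the control rate.

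For safety review reports the same section uses another construction. The ratio is shown with a provider-level bootstrap interval, at a percentile set by Pocock alpha spending, and with 1.5 for reference. The rule, for ED and urgent care visits together and with a limit of 1.5, is then: "Excess harm is observed if the entire coverage of the confidence interval for the rate ratio comparing the greater to the lesser rate" lies above that limit. No action is attached to this finding. Neither the overall interim alpha nor the number of looks is given; section 9.1.1 expects three reports a year.

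Section 10.2 first allows the IRB, NIMH or the NIMH DSMB to require a halt. It then says: "The PI may temporarily suspend enrollment pending review by these authorities if warranted based on significantly more safety events occurring in the intervention arm". It adds: "The study would not be halted early if the intervention was found to be protective". It does not mention 1.5 or define what counts as significantly more events.

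On the between-arm safety comparisons, section 10.1 says: "The PI and site investigators will be blinded to the results of these assessments". Section 5.3.2 keeps the PI blinded to arm until follow-up is complete and leaves preparation of the harm reports to unblinded data coordinating centre staff. The SAP has no interim harm rule; its Secondary analysis I covers only the final comparison with 1.5.

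**The concern.** Three things do not fit together.

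- **Direction.** A ratio of the greater to the lesser rate is always at least 1. An intervention that cuts ED and urgent care visits enough would therefore carry the excess harm label, while section 10.2 treats the same result as protective.
- **Sensitivity.** Requiring the whole interval to lie above 1.5 means the observed ratio must be well above 1.5 before anything is flagged. Ratios the protocol regards as too high may not trigger the label.
- **Trigger and route.** Section 10.2 uses another criterion and gives the PI a discretionary step that depends on results the PI is not meant to see.

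This matters because section 10.1 says incidental adverse events cannot be compared between arms, so the comparisons of routinely recorded events carry the harm monitoring. Under Protocol 8.2.1 the final ED non-inferiority test is done only if the primary endpoint shows superiority. If it does not, the interim rule is the only formal ED criterion the protocol leaves.

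**Working it through.** **Inputs (Protocol 8.2.1 and section 4).** Control ED rate 0.0325 per month, alternative 0.05; 400 per arm, or 360 after 10% loss; 6 months of follow-up; margin 1.5; non-inferiority power calculated "with a one-sided 0.025 alpha level with equal allocation between groups".

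**Reproducing the plan's power.** Expected events per arm are E = n × 6 × rate. Power at a true ratio of 1 is Φ(ln 1.5 / √(2/E) − 1.96).

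- 0.0325, 400 per arm: E = 78, power 71.6% (stated 71%)
- 0.0325, 360 per arm: E = 70.2, power 67.1% (stated 67%)
- 0.05, 400 per arm: E = 120, power 88.1% (stated 88%)
- 0.05, 360 per arm: E = 108, power 84.6% (stated 84%)

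The same Poisson model is therefore a fair basis for the harm rule.

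**Written rule, one look at full data.** With true ratio R and an unadjusted 95% interval, SE = √(1/E + 1/(E·R)) and P(flag) = Φ((ln R − ln 1.5)/SE − 1.96).

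- R = 1.75, E = 78: SE = √(1/78 + 1/136.5) = 0.142; Φ(0.154/0.142 − 1.96) = Φ(−0.87) = 19%.
- R = 2.0, E = 78: SE = √(1/78 + 1/156) = 0.139; Φ(0.288/0.139 − 1.96) = Φ(0.11) = 55%.
- R = 2.0, E = 120: SE = √(1/120 + 1/240) = 0.112; Φ(0.288/0.112 − 1.96) = Φ(0.61) = 73%.

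For the unadjusted lower limit to pass 1.5, the observed ratio must reach about 1.97 at 0.0325 per month, or 1.87 at 0.05.

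**Written rule, repeated looks.** This was simulated with 100,000 trials per scenario. Assumptions the protocol does not supply: two-sided 0.05 overall, Pocock-type spending, uniform enrolment over 24 months, eight looks (every 4 months, the last at month 30), Wald intervals in place of the bootstrap, and no clustering. Five- and six-look schedules differ by at most about 1.5 points.

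Probability of a flag in the harm direction, 400 per arm:

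| True ratio | 0.0325, one look | 0.0325, eight looks | 0.05, one look | 0.05, eight looks |
|---|---|---|---|---|
| 1.5 | 2.5% | 1.9% | 2.5% | 2.0% |
| 1.75 | 19% | 13% | 27% | 19% |
| 2.0 | 55% | 43% | 73% | 63% |
| 2.25 | 85% | 77% | 96% | 93% |
| 2.5 | 97% | 95% | over 99% | over 99% |

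With 360 per arm at 0.0325, the eight-look figures are 12% at 1.75 and 38.5% at 2.0. Early flags are weaker: at 0.0325 and 400 per arm, a true ratio of 2.0 is flagged by month 12 in 10.6% of trials.

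**Clustering.** Multiplying the variance by an assumed design effect of 2 lowers the one-look figure at 2.0 and 0.0325 from 55% to 31%.

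**Direction.** Suppose the intervention truly halves visits: 78 control and 39 intervention events. Greater over lesser is 2.0, SE = √(1/78 + 1/39) = 0.196, and P(flag) = Φ(0.288/0.196 − 1.96) = Φ(−0.49) = 31% at one unadjusted full-data look. A true halving would be labelled excess harm about three times in ten.

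**Section 10.2 for comparison.** If significantly more events is read as a lower limit above 1 in the intervention direction, the eight-look probability at 0.0325 and 400 per arm is 70% at a true ratio of 1.5 and 96% at 1.75, with about 2% at 1.0. The written rule gives 2%, 13% and about 0%. This reading is an assumption. It shows how far apart the two passages may be, not which is right.

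**The case against.** The strongest reply has five parts.

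1. A reader might take 1.5 as already unacceptable and cite the 2.5% flag rate there as missed harm. The protocol says it is the value "beyond which" results are unacceptable only in the sense quoted above, and it calls the matching 0.0488 per month the maximum acceptable rate. The flag rate at exactly 1.5 is therefore boundary error by construction. This stands, and the sensitivity point rests on 1.75 and 2.0 instead.
2. A reader might infer that suspension is left to a blinded PI. It is not. Under section 10.2 the IRB, NIMH or DSMB can require a halt, section 9.2 lets NIMH, the DSMB or the IRB terminate, and the DSMB receives the arm comparisons three times a year. The PI step is optional, temporary and pending review by those bodies. What remains is that the documents do not say how a blinded PI would come to take it.
3. A reader might infer that real harm would usually go unflagged. That is too broad. Without clustering, ratios of 2.25 and above are usually flagged by the end, as is a doubling at 0.05 per month. The reports also show the ratio and interval whether or not the label fires, and cover hospitalisations, suicide attempts and deaths.
4. A reader might call sections 8.2.1 and 10.2 contradictory on threshold. Section 8.2.1 defines a finding and section 10.2 concerns action, and the latter's trigger may even refer to the former. The passages are unreconciled, which is a lesser fault.
5. The DSMB charter and report template may settle some of this. They are not among the documents, so that cannot be confirmed or excluded.

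On direction, section 10.2 already rules out halting for a protective result. That limits the consequence but leaves the label wrong.

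**Conclusion.** The point holds in limited form. The interim definition is direction-free and can label a benefit as excess harm. It is insensitive moderately above the protocol's own limit: about 13% to 19% at a true ratio of 1.75 and 43% to 55% at 2.0, with 0.0325 visits per month and 400 per arm; at 0.05 per month a ratio of 2.0 is flagged 63% to 73% of the time. The lower end of each range is the eight-look simulation and the upper end a single unadjusted look at full data. Section 10.2 uses a different, undefined trigger and gives the PI a step that rests on information the PI is blinded to.

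The figures assume Poisson counts, no clustering, and the look schedule and overall alpha stated above. They use an ED-only rate, whereas the rule counts ED and urgent care visits together. A higher combined rate would raise the probabilities, and clustering by provider would lower them. The documents do not support saying that harm monitoring as a whole fails, because the DSMB sees the comparisons and can act.

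**What to change.** Reconcile Protocol 5.3.2, 8.2.1, 10.1 and 10.2 so that they describe one arrangement:

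- Define the interim ratio as intervention over control, as in the final analysis.
- In each safety report, show the interval against both 1.0 and 1.5.
- State the rule's operating characteristics for ED plus urgent care visits, giving the overall alpha, number of looks, combined rate and clustering assumed.
- Say how the finding in 8.2.1 relates to the trigger in 10.2, and define that trigger.
- Reconcile the PI's suspension step with the PI's blinding, given that unblinded coordinating centre staff prepare the reports and the DSMB receives them.

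No halting threshold is proposed. That is a trade-off for the DSMB, which keeps the decision. The cost is protocol and report-template wording plus a short calculation. The small downside is that a reference line at 1.0 is crossed more often and needs DSMB judgement.

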5.2 Patients and Families: Inclusion and Exclusion Criteria for Patient Subjects

Potentially eligible patients are logged for study enrollment at the time the medication alert fires. Patients are assigned to the study arm of the randomized prescribing provider. Local study staff will blindly confirm eligibility via medical record review for all intervention and control arm patients logged for eligibility review and enrollment.

Inclusions:

- Patient is ≥ 3 and < 18 years of age at the time of the encounter at which the study alert fired;
- Study service (BH navigation, bridging therapy, CAP consult) ordered in Epic for the patient;
 - The BPA allows providers to remove the antipsychotic order and still order services.
- Patient is initiating a new episode of outpatient treatment with an antipsychotic medication.
 - New episodes are defined by no record of an antipsychotic medication being ordered within the health system as part of an outpatient care plan in the prior 180 days.

Exclusions:

- Patient has a diagnosed psychotic disorder, mania, autism spectrum disorder, or intellectual disability;

- Patient was enrolled in the SUAY pilot study;
- The antipsychotic entered is prochlorperazine (Comazol®) – which is used to treat nausea;
- An outpatient antipsychotic order is entered by a temporary provider in the health system. For example, a “doc of the day” signing an order initiated by a pharmacist transferring an existing prescription to the health system. This situation may also occur when a temporary provider signs a medication order for a prescription initiated in an inpatient setting as part of a discharge plan.
 - Note that orders placed by temporary providers do not count towards the 180 day medication free period for defining a new episode of care.
- The antipsychotic order was placed within an urgent care, emergency department, or inpatient setting (to avoid intervening during a crisis).
 - Note that orders placed in these settings do not count towards the 180 day medication free period for defining a new episode of care.
- Primary language is not English (e.g., patient requires a translator).

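### Protocol 8.2.1 claims more than 95% power for a 6% reduction from 95% use with 720 patients; its own table gives 80% for that case, and recalculation gives 84.5%

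*Protocol*

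**What the plan says.** Protocol section 8.2.1 expects 800 patients, of whom 720 remain at 6 months. Section 8.1 gives this as up to 400 and 360 per arm. With alpha 0.05 and 95% antipsychotic use under control, the text says that "this sample will ensure over 95% power to detect a 6% reduction in the percent of participants with any order for antipsychotic medications".

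Two further power statements for the same outcome follow. For subgroups, "we expect to have 80% power to detect a 13% reduction in subgroups with exposures occurring with 25% prevalence", and likewise 80% for a 17% reduction at 18% prevalence. For the pre-specified minimal clinically important difference, "We have over 90% power to detect a 10% reduction in antipsychotic use at 6 months", at control rates of 85, 90 or 95%.

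The text then says "we provide examples of detectable intervention effects corresponding to alternative scenarios in the table that follows". The table is titled "Power under varying percentages of participants in each arm taking antipsychotic medication at 6 months" (based on orders, with various subgroup prevalences). Its first row reads 100% prevalence, 360 per arm, 89% intervention, 95% control, power 80%.

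On design, section 5.2 says "Patients are assigned to the study arm of the randomized prescribing provider". For the interim emergency department (ED) intervals, section 8.2.1 says "Resampling will be done on the cluster (provider) level". For ED non-inferiority it says "we estimate 71% power(48) with 400 patients per arm and 67% power with 360 patients per arm".

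**The concern.** The text and the first table row describe the same case: the same control rate, the same 6-point difference and the same 720 patients. One says more than 95% power, the other 80%. Both cannot be right, and no outside figure is needed to see it.

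The SAP has no power calculation, so section 8.2.1 is the only source. The statement also bears on a second test, because the protocol assesses ED non-inferiority at final analysis only if superiority is shown on antipsychotic use at 6 months. A reader relying on the text would put the chance of missing a true 6-point effect below 5%. The table implies 20%, and direct calculation about 16% (100 − 84.5 = 15.5).

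A smaller matter is that prescribers are randomized and the analysis allows for clustering, yet no allowance for it is visible in the power figures.

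**Working it through.** **Inputs (protocol 8.1 and 8.2.1).** Control rate p2 = 0.95; intervention rate p1 = 0.89; n = 360 per arm; alpha 0.05. Sidedness is not stated for this outcome; two-sided is assumed first.

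**Formula.** Power = Φ[(d − z·SE0)/SE1], where d = p2 − p1, SE0 = √(2·p̄(1−p̄)/n), SE1 = √((p1q1 + p2q2)/n), q = 1 − p, and p̄ is the mean of the two rates.

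**Step 1: does this formula match the table?** The stated rates were entered for all eight rows.

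| n per arm | Rates | Stated | Computed |
|---|---|---|---|
| 360 | 89 vs 95 | 80% | 84.5% |
| 360 | 85 vs 95 | >99% | 99.5% |
| 360 | 80 vs 90 | 97% | 96.5% |
| 360 | 75 vs 85 | 92% | 92.0% |
| 90 | 82 vs 95 | 80% | 78.5% |
| 65 | 78 vs 95 | 80% | 81.7% |
| 36 | 75 vs 95 | 67% | 66.8% |
| 18 | 65 vs 95 | 62% | 62.3% |

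Seven rows agree within 2 points, with patients treated as independent. The first row is 4.5 points off.

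**Step 2: the disputed case.** d = 0.06 and p̄ = 0.92. SE0 = √(2 × 0.92 × 0.08/360) = 0.02022. SE1 = √((0.89 × 0.11 + 0.95 × 0.05)/360) = 0.02010. Then (0.06 − 1.96 × 0.02022)/0.02010 = 1.013, and Φ(1.013) = 84.5%.

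**Step 3: can any reading reach 95%?** A relative 6% reduction means 0.95 × 0.94 = 89.3%.

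| Reading | 360 per arm | 400 per arm |
|---|---|---|
| 89%, two-sided | 84.5% | 88.0% |
| 89.3%, two-sided | 81.3% | 85.2% |
| 89%, one-sided | 90.8% | 93.2% |
| 89.3%, one-sided | 88.6% | 91.3% |

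Other methods at 89 vs 95, 360 per arm, two-sided: unpooled 84.8%, arcsine 85.6%, log risk ratio 83.9%, log odds ratio 82.6%, Fisher 82.1%, continuity-corrected 80.9%. The highest value found is 93.8% (arcsine, one-sided, 400 per arm). Power of 95% needs about 529 per arm at 89%, or an intervention rate of about 87.4% at 360 per arm. Only taking 720 as the number per arm passes 95% (98.8%), and the protocol is clear that 720 is the total.

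**Step 4: where could 80% come from?** Solving for 80% power against 95% control gives 89.41% (n = 360), 81.69% (n = 90) and 78.49% (n = 65). These round to the printed 89, 82 and 78 in the three 80% rows. Rates that round to 89% (88.5 to 89.5%) give 88.8 to 78.9% power, a range that contains 80% and excludes 95%.

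**Step 5: the 10% difference.** Rows 2 to 4 give 99.5, 96.5 and 92.0%, so the claim of over 90% reproduces under independence.

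**Step 6: clustering.** The n is 400 × 0.9 = 360, with no inflation. The ED figures also reproduce with plain Poisson counts: events per arm = rate × 6 × n, SE = √(2/events), power = Φ(ln 1.5/SE − 1.96). At 0.0325 per month, 70.2 and 78.0 events give 67.1 and 71.6% (stated 67 and 71%). At 0.05, 108 and 120 events give 84.6 and 88.1% (stated 84 and 88%).

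**The case against.** **It changes nothing in the trial.** The sentence does not set the sample size and enters no estimate, interval or decision rule. The planning benchmark is the 10% difference, which reproduces. This stands, and it limits the point to correcting the record. It does not make the stated power true.

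**The table may not be right either.** At exactly its printed rates, row 1 should read about 84%. The rounding explanation fits all three 80% rows, but it is an inference. A continuity correction (80.9%) or a relative reduction (81.3%) would also land near 80%, and the protocol names no formula for this outcome. This stands too. A reader might infer that the table is certainly correct; the documents do not say so. What is established is that the text figure is wrong under every reading tried.

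**Analysing all 400 per arm might offset some loss.** This cannot be relied on. Under Primary analysis I, the SAP makes no adjustment for disenrollment in the binary outcome, so a disenrolled patient without orders reaching day 181 counts as a non-user. As an illustrative extreme, if the 10% lost all counted so in both arms, the rates become 0.9 × 89 = 80.1% and 0.9 × 95 = 85.5%, and power at 400 per arm is about 53% with no clustering at all.

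**Clustering is handled in the analysis.** It is, through provider-level GEE with robust errors. A reader might infer that the trial is underpowered because of clustering. The documents do not support that: the visible text gives no intraclass correlation, cluster size or design effect, and the note behind the asterisk on the table's n-per-arm heading is not visible.

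**Conclusion.** The power stated for a 6% reduction is wrong as written: more than 95% in the text, 80% in the protocol's own table, and 84.5% by direct calculation at exactly 89 vs 95% with 360 per arm, two-sided, independent patients. The contradiction itself rests on no assumption. The 84.5% rests on the normal two-proportion formula and the two-sided test.

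A reader might go further and conclude that the sample is too small. That does not follow: the 10% claim holds under independence, and the 6% statement does not drive the sample size.

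The clustering part is a minor reporting gap. Its size cannot be computed from the documents. For orientation only, assumed design effects of 1.2, 1.5 and 2.0 applied to 360 per arm would give 77, 68 and 56% for 89 vs 95, and 87, 78 and 66% for 75 vs 85.

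**What to change.** 1. In protocol 8.2.1, replace the figure of more than 95% with one that agrees with the table. If row 1 is a rounded detectable difference, state about 80% and add that the unrounded rate is about 89.4% against 95%. If exactly 89 vs 95% is meant, put about 84% in both the text and row 1. The authors know which was intended.
2. Name the formula and the sidedness for this outcome.
3. Minor: state that the power figures assume no clustering (plain Poisson counts for ED visits), and that conservative in 8.2.1 and 8.3 refers only to disenrollment. Any design-effect range shown should be labelled as an assumption.

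The cost is one figure and two or three sentences. The stated power becomes less favourable. No patients are added and no analysis changes.
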